d. Significance Testing and Preliminary Analyses: All tests for main effects will be performed at twotailed significance α =5%. Before performing specific analyses (described below), we will examine all variables for outliers. The distributions of all continuous variables will be checked for normality, and transformations will be employed, if necessary, before applying specific parametric techniques. The distribution of demographic variables (ethnicity, gender, age) and other covariate measures of at baseline in the treatment arms will be examined and described in terms of means, standard deviations, proportions and 95% confidence intervals. The covariates (specified in Section 3.a.iii) may be associated with treatment outcome. For this reason, we will adjust for these covariates in all models used to test the study hypotheses. These covariates will be included in all models as main effects regardless of their statistical significance or whether they differ between treatment groups. In the secondary analyses, we will adjust also for baseline value of the outcome variable where appropriate. This adjustment will be based on the inclusion of main effects for the baseline.

e. Hypotheses Testing i. Primary hypotheses:

Hypothesis 1: Nabilone and XR-NTX will significantly increase time to relapse as compared to placebo. The following Cox Proportional Hazards model will be used: (1) $\log{hi(t)} = \log{h0(t)} + \beta 1 I J + \beta 2 U J J$ where hij(t) is the hazard for individual i in the treatment group j at time t; h0(t) is the baseline hazard function; Uj is the vector of covariates; and I J is the indicator variable for treatment with nabilone and XR-NTX. Significant I J indicates that the hazard rate of each treatment group is different. ii. Secondary hypotheses:

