Hypothesis 2: Nabilone and XR-NTX will significantly promote abstinence from cannabis use as compared to placebo during the final 2 weeks of study (weeks 11 and 12). The following logistic regression model will be used: (2) logit(Yij = 1) = $\beta 0 + \beta 1$ Ij + $\beta 2$ Uij + ϵ ij where Yij is a dichotomous measure indicating whether the i th subject in the treatment group j has used cannabis during the final 2 weeks of study, with Yij = 1 for non-abstinent and Yij = 0 for abstinent during the final 2 weeks of study; Uij is the vector of all appropriate covariates; Ij is the indicator variable for treatment with nabilone and XR-NTX; and ϵ ij is a random error term. Significant Ij indicates that the odds of abstinence from cannabis during the final 2 weeks are different in each group.

Hypothesis 3: Nabilone and XR-NTX will significantly increase time to dropout as compared to placebo. To test the secondary hypothesis 3, we will use the same model as in (1) to test whether retention is different between the two groups.

Hypothesis 4: Over time, the days of weekly cannabis use will be significantly less in the Nabilone and XR NTX group as compared to the placebo group. This hypothesis will be tested using the following

longitudinal mixed effects model: (3) Yijt = $\beta 0 + \beta 11j + \beta 2t + \beta 3t^*1j + \beta 4Uij + sij + \epsilon ijt$ where Y ijt is the days of cannabis used over a one-week period by the i th subject in the treatment group j at week t (t =1, 2, ..., 12); Uij is the vector of covariates; Ij is the indicator variable for treatment with nabilone and XR-NTX; sij is a random intercept for subject i and ϵijt is a random error term. Significant interaction t*Ij indicates that the effect of each treatment group is different over time (that corresponds to rejecting null hypothesis that $\beta 3= 0$). If so, the effect of time will be estimated for each group separately and the groups will be compared (using contrast) in the last time point t=12. If the interaction term is not significant (i.e., the difference between the treatment arms does not change over time), we will refit the model without the interaction term and test the significance of the main effect of treatment (i.e. rejecting the null hypothesis that $\beta 1 = 0$).

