Hypothesis 5: Over time, subjects in the nabilone and XR-NTX group will experience significant reduction in the pattern of cannabis withdrawal symptoms (measured as mean Marijuana Withdrawal Checklist score per week) compared to the subjects in the placebo group.

Hypothesis 6: Over time, subjects in the nabilone and XR-NTX group will exhibit significantly reduced cannabis cravings (as measured by Marijuana Craving Questionnaire) compared to subjects in the placebo group.

Hypothesis 7: Over time, subjects in the nabilone and XR-NTX group will experience significantly less sleep disturbance (as measured by the Medical Outcomes Study Sleep scale) compared to subjects in the placebo group. To test the secondary hypotheses 5, 6, and 7 we will use the same model as in (3) where Yijt is the appropriate outcome variable (as specified for each hypothesis) for the i th subject in the treatment group j at week t (t =1, 2, ..., 12). We will first test the interaction effect of group and time as described for Hypothesis 4.

iii. Exploratory Analyses We will explore whether there are differences between the two groups with respect to the number of adverse effects, side effects, and tolerability in relation to the primary outcome. We will also explore whether co-occurring psychiatric disorders, gender, concurrent treatment exposure, trauma history, or impulsivity are predictors of treatment outcome.

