C. DATA MANAGEMENT AND ANALYSIS C1. Data Acquisition and Transmission Research assistants trained in behavioral observation techniques will assist in data collection during laboratory sessions. Subjective responses, performance effects, food intake and sleep will be obtained electronically using our custom-designed software programs. Some data (e.g., sleep questionnaires) will be recorded manually, and then entered into an Excel spreadsheet. C2. Data Entry Methods As noted above, a portion of the data is automated and a portion is recorded on data sheets, and transferred manually to an Excel spreadsheet. C3. Data Analysis Plan Subjective effects, food intake, sleep, and task performance will be analyzed using repeated measures analysis of variance (ANOVA) models with planned comparisons calculated with SUPERANOVA, SPSS or SYSTAT packages. We will use a cluster analysis of peak subjective effects ratings to reduce the overall number of comparisons (Haney et al., 2013a,b). Tests of differences will be based on F-statistics with degrees of freedom corrected, depending on the observed within-subject correlation of the measures, using the method of Huynh and Feldt. Planned contrasts will be single degree of freedom comparisons using the appropriate interaction error term. Results will be considered statistically significant at p < 0.05, using 2- tailed tests. The primary analyses in this study will be on the intent-to-treat (ITT) sample, i.e. on all randomized patients. Cannabis consumption and cannabis abstinence, are assessed repeatedly over time and we will try to collect them at all study assessment points. We will account for unobserved data by examining the primary outcome variables using longitudinal mixed effects models (MEM) (Brown & Prescott, 1999; Diggle, et al., 2002) using PROC GLIMMIX in SAS[®]. MEMs do not require complete measurements data to estimate the outcome variable. The inferences from analyses with missing data are valid provided that they are "missing at random" (Little & Rubin, 2002). 'Missing at random' (i.e the missing mechanism does not depend on the value of the unobserved outcome) is untestable in most medical research and in our study as well. One can assume either parametric or semiparametric models for the missingness that does depend on the unobserved outcome value and do the analysis (Diggle & Kenward, 1994; Kenward, 1998; Liu, et al., 1999; Rotnitzky, et al., 1998; Scharfstein, et al., 1999). Comparison of the inferences from assuming various models for the missingness provides a measure of the validity of the efficacy estimate from the model that assumes missing 'at random'. One can also compute a local sensitivity index which measures the change in the estimated treatment effect in a neighborhood of the 'missing at random' model for missingness (Rotnitzky, et al., 2001). We plan to perform a sensitivity analysis based on these two approaches to assess the effect of the assumption of missing 'at random' on the inference.

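### Hypotheses 4-7 are tested by interaction and then main effect with no stated deciding result, so the nominal 5% is about 5-8% or 9.75% depending on the reading

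*SAP*

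**What the plan says.** SAP section 3.e.ii, Hypothesis 4, sets out model (3): a linear mixed model for weekly days of use over weeks 1 to 12, with treatment, linear time, their product and covariates. The only random effect is an intercept ("sij is a random intercept for subject i").

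Testing goes in two steps. The interaction comes first: "Significant interaction t*Ij indicates that the effect of each treatment group is different over time". If it is significant, time effects are estimated by arm and "the groups will be compared (using contrast) in the last time point t=12". If it is not, the SAP takes the difference between arms to be unchanging and "we will refit the model without the interaction term and test the significance of the main effect of treatment".

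Hypotheses 5 (withdrawal), 6 (craving) and 7 (sleep) take over the procedure: "We will first test the interaction effect of group and time as described for Hypothesis 4".

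On levels, section 3.d says "All tests for main effects will be performed at twotailed significance" of 5%. No level is given for the interaction. Section C3, on the repeated-measures ANOVA, has "Results will be considered statistically significant at p < 0.05, using 2- tailed tests". The SAP neither allocates the 5% across the two steps nor says which result supports the hypothesis.

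**The concern.** Each hypothesis can be supported along two routes, and the second is tried only when the first fails. If a rejection on either route counts, the procedure has two chances at 5%, and its level is not 5%. If the week-12 contrast decides the first route, the excess is smaller, but the SAP leaves that choice open until the data are seen.

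The refit also rests on reading non-significance as absence. With 36 patients per arm (section 3.b) or 40 (section A4), failing to reject the interaction does not show that the arms differ by a constant amount. Protocol Table 2 gives full dosing to week 7, a taper in week 8 and no study medication in weeks 9-12, so a constant difference over weeks 1-12 is not what one would expect of an effective drug.

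At stake is how far positive findings on days of use, withdrawal, craving and sleep can be trusted. Withdrawal matters most: the protocol and SAP section A2 list it as a primary outcome, and the protocol makes the checklist used in Hypothesis 5 its main withdrawal measure.

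**Working it through.** **Inputs.** Main-effect level 5% two-sided (3.d). Interaction level 5%: assumed. Twelve weekly values, linear time, random intercept (model 3). 72 or 80 patients (3.b, A4). Intraclass correlation (ICC): not in the documents, taken as 0 to 0.7. Retention over 12 weeks: 100% in both arms, 50% in both arms, or 15% v 40% (close to the rates in the power sections).

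**Step 1: the plan's own level.** In a null simulation of model (3) with complete data (40,000 trials per setting), the interaction test alone rejected in 4.8-5.0% and the main-effect test alone in 5.0-5.2%. Each single test holds its 5%.

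**Step 2: either rejection counts.** When there is no effect, the interaction estimate is an unbiased estimate of zero. The refitted main effect is the efficient estimate in the smaller model, so the two are uncorrelated if the random-intercept covariance is right. A direct covariance calculation gave correlation 0.000 for every ICC and dropout pattern tried. Hence

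P(reject) = 1 - 0.95 × 0.95 = 9.75%.

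The simulation gave 9.6-9.9%. Rejections favouring the drug were 4.7-5.0%, against 2.5% for one two-sided test.

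**Step 3: the week-12 contrast must confirm a significant interaction.** With complete data the week-12 difference equals the mean difference plus 5.5 times the slope difference, because week 12 lies 5.5 weeks from the mean time of 6.5. The sum of squared deviations of weeks 1-12 is 143. The squared correlation between the contrast and the interaction estimate is therefore

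ρ² = a / (a + ICC + (1 - ICC)/12), where a = 30.25 × (1 - ICC)/143.

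At ICC 0.5: a = 0.1058, ρ² = 0.1058/0.6474 = 0.163, ρ = 0.40. Then P(reject) = 0.05 × 0.95 + P(interaction and contrast both significant):

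| ICC | ρ | both significant | P(reject), complete data | P(reject), with dropout |
|---|---|---|---|---|
| about 0 | 0.85 | 2.5% | 7.3% | 7.4-8.2% |
| 0.3 | 0.54 | 1.1% | 5.8% | 6.3-7.2% |
| 0.5 | 0.40 | 0.7% | 5.4% | 5.8-6.5% |
| 0.7 | 0.28 | 0.5% | 5.2% | 5.4-5.8% |

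The dropout column covers both sample sizes and both dropout scenarios, with one generated dropout pattern per setting. In simulation with complete data, rejections favouring the drug were 2.6-3.5%.

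**Step 4: constancy and the dosing schedule.** Suppose, as an illustration only, a difference d in weeks 1-8 and none in weeks 9-12. The 12-week average is 8d/12 = 0.67d. The fitted slope is -16d/143 = -0.112d per week, and the fitted week-12 difference is 0.67d - 5.5 × 0.112d = 0.05d. The interaction is real here. If it misses significance, the refit reports 0.67d as though it applied throughout; if it is significant, the week-12 contrast looks at almost nothing.

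**The case against.** The strongest reply is that the week-12 contrast is the planned comparison on the first route. Hypothesis 4 predicts less use on active treatment, and a significant interaction alone cannot show that. This is a natural reading, and it brings the rate down to 5.2-5.8% with complete data and ICC of 0.3 or more. It stands as a reason to report a range: a reader might infer a flat rate of nearly 10%, and the documents do not support that without the condition that either rejection counts. But the SAP does not make the contrast decisive, and even so the rate exceeds 5%.

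Other objections stand in part:

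- The 5% for the interaction is inferred. At 10% the either-rejection rate would be 1 - 0.90 × 0.95 = 14.5%.
- The rates count both directions. A reader might take 9.75% as the chance of a false claim of benefit; that chance is about half.
- A reader might compound the rate over four hypotheses. The outcomes come from the same patients and are unlikely to be independent, and Hypothesis 7 uses a sleep scale absent from the protocol's assessment schedule, which lists the PSQI.
- Section 3 names nabilone and XR-NTX. The clonazepam sections list other secondary outcomes and assign ANOVA to subjective effects and sleep. Yet section 3 is filed under this study, C3 calls for mixed models without writing one, and model (3) is the only one written out.
- With balanced data the refitted coefficient still estimates the time-averaged difference. That is true, and it limits the harm to the estimate; it does not justify calling the difference constant.
- The Cox analysis of relapse is untouched.

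**Conclusion.** The point holds as a fault in the decision rule. Provided section 3 supplies the clonazepam secondary analyses and the interaction is tested at 5%, the two-sided false-positive rate per hypothesis is 9.75% if either rejection counts. It is about 5-8% if the week-12 contrast must confirm a significant interaction. False claims of benefit are about half of each. The SAP does not say which rule applies. Separately, a non-significant interaction at this sample size does not establish a constant difference, and the dosing schedule argues against one.

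These rates assume that the random-intercept model is correct. If true slopes vary between patients (assumed SD 0.03-0.10 per week in units of total SD, ICC 0.5, 72 patients), the either-rejection rate rises to about 12-30%. That is a further weakness of the model and is not counted here.

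This should be corrected, but it mainly concerns secondary hypotheses in an early Phase II trial.

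**What to change.** For each of Hypotheses 4-7, name one treatment contrast from the model that keeps the interaction, with its favourable direction stated. It could be the time-averaged difference or the difference at a pre-named week, chosen with the taper and medication-free weeks in mind. Make it the only test that decides the hypothesis, at two-sided 5%. Delete the refit step and report the interaction descriptively.

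A joint two-degree-of-freedom test of treatment and interaction has no direction, so it cannot by itself show less use. It may serve as a gatekeeper, with the named contrast deciding. The SAP should also state whether these hypotheses apply to clonazepam and on which sleep instrument.

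The cost is SAP wording, and some power against effect patterns that the chosen contrast does not target.

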## **Specific Aims and Hypotheses**

#### Specific Aims and Hypotheses

#### Primary Outcome Measure:

(1) Cannabis withdrawal (mood, sleep quality and duration, food intake)

(2) Cannabis relapse defined as (1) time to any MJ use as recorded by the timeline follow back method and

confirmed by urine metabolite levels, or (2) time to dropout, whichever comes first, and (3) medication compliance (% of pills taken) or time to discontinuation. Participants who relapse will continue in the trial to obtain secondary outcome measures.

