## Secondary Outcome Measures:

(1) Abuse liability (medication liking, desire to take again)

(2) Cognitive task performance

(3) Side effects and tolerability.

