## **Study Procedures**

Describe the procedures required for this study

*Study Participants*: Participants will be 80 men and nonpregnant women with CUD who report using cannabis a minimum of 5 days per week over the past 28 days. The minimum threshold of a near-daily pattern of cannabis use will select a population with moderate-to-severe CUD. This level of severity is consistent with the sample in our previous clinical trial (Levin et al. 2011), and, we suspect, typical of individuals with CUD who seek treatment. This sample is less likely to achieve abstinence spontaneously or in response to non-medication aspects of the trial (e.g., general therapeutic support), and thereby minimize the placebo response rate. Selecting for near-daily cannabis users will also prevent a "floor effect" (i.e., participants using cannabis infrequently at baseline would be unlikely to demonstrate significant improvement).

**Inpatient phase**: Patients seeking cannabis treatment will move into the inpatient unit at NYSPI for 5 nights. On move-in day, participants will only receive the PM capsule administration; all capsules will be given under observation and will be double blind. During the next 4 days (days 2-5; Table 1), we will measure medication effects on cannabis withdrawal, including measures of mood, cannabis craving,

objective and subjective measures of sleep, and food intake in our Outpatient Marijuana Laboratory. Cannabis relapse measures will begin following discharge on day 6.

**Outpatient phase**: After discharge from the inpatient phase, 12-weeks of outpatient treatment will be conducted (Table 2). Study visits will occur twice weekly. One visit per week will be with the research psychiatrist for a Medical Management session to perform study assessments and to monitor medication effects and compliance. Participants will have a manual-guided (Pettinati et al. 2005) supportive behavioral treatment session with the research psychiatrist each week. This psychosocial intervention facilitates compliance with study medication and other study procedures, promotes abstinence from cannabis and other substances, and encourages mutual-support group attendance. The second visit each week will be for vital sign monitoring, urine toxicology and completion of self-report measures. Participants will be given cash incentives contingent on study visit attendance and completing other study procedures with the objective of achieving a high treatment adherence.

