*Clinical Status*: The Clinical Global Impression Scale-Observer (CGI; Guy 1976) will be used to measure the overall clinical status of the participant as well change from baseline in symptom severity. The Clinical Global Impression-Self (CGI-S) is a two-item scale that asks the subject to rate his or her current level of symptoms and estimate changes from baseline (Guy 1976).

Cognitive, Behavioral and Impulsivity Measures: A series of cognitive and behavioral measures will be performed at baseline, end of active medication treatment (week 8), and end of the observation period (week 12), to explore potential therapeutic mechanisms of action of the medication treatment.

Concurrent Treatment measure: The Modified Treatment Services Review assesses the past-week exposure to health care, psychiatric, or substance use disorder treatment (McLellan et al. 1992).

Medication Adherence measures: The Structured Pill Count Interview is a timeline followback assessment of study medication compliance accounting for each dose of prescribed study medication. Fluorometric detection of a urinary riboflavin concentration (Herron et al. 2013) will be used as a biological method to determine compliance with study medication.

Anxiety measure: A structured-interview version of the Hamilton Anxiety Scale (HAM-A; Hamilton 1959) will be used to assess mood and anxiety symptoms at baseline and changes associated with treatment.

Psychiatric Evaluation and Diagnosis: The MINI International Neuropsychiatric Interview will be performed during screening as part of a complete psychiatric diagnostic assessment.

Sleep measure: The Pittsburgh Sleep Quality Index Scale (PSQI; Buysse 1989) will be the primary outcome of sleep quality and length.

Please attach copies, unless standard instruments are used outpatient study assessments 5-24-16.pdf

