## Table 3: Outpatient Study Assessments

	X once weekly; XX twice weekly	Screening	Baseline	Week 1	Week 2	Week 3	Week 4	Week 5	Week 6	Week 7	Week 8	Week 9	Week 10	Week 11	Week 12
	Medical History and Physical Examination	x													
	Pregnancy, serum	x													
	Pregnancy, urine		x				х				х				х
	Psychiatric Evaluation	x													
5	Serum Laboratory Examination	x					х				х				х
latic	Urinalysis	x					х				х				х
Medical Evaluation	Urine Toxicology	x	x	х	X X	x x	x x								
dical	Urine Fluorometry (quantitative riboflavin)			x	X X	X X	x x								
Med	Vital signs (weight, pulse, blood pressure, and temperature)		x	x	X X	x x	x x								
	CIWA-BZD									Х	Х	Х	Х		
	Clinical Global Improvement Scale (CGI)- Observer		x	х	x	x	х	х	x	x	х	x	х	x	x
	C-SSRS	x	x		x		х		х		х		х		х
	Hamilton Anxiety Scale (HAM-A)		x		x		х		х		х		х		х
Interview	MINI International Neuropsychiatric Interview	x													
ter	Structure Pill Count Interview			х	x	x	х	х	х	x	х	х	х	х	х
_	Systematic Assessment for Treatment and Emergent Events (SAFTEE)		x	x	x	x	x	x	x	x	x	x	х	x	x
	Timeline Follow-Back (TLFB)	x	x	х	x	x	х	х	х	x	х	х	х	х	х
	Treatment Services Review (TSR)		х	х	x	x	х	х	х	x	х	х	х	х	х
	Clinical Global Impression (CGI)-Self		x	х	x	x	х	х	x	х	х	х	х	х	х
Self- Report	Marijuana Craving Questionnaire (MCQ)		х	х	x	x	х	х	х	x	х	х	х	х	х
Se Rep	Marijuana Withdrawal Checklist (MWC)		x	х	x	x	х	х	x	x	х	х	х	х	х
	Pittsburgh Sleep Quality Index (PSQI)		х	х	х	х	х	х	х	х	х	х	х	х	х

Tabl	e 1: Inpatient F					
Day	1	2	3	4	5	6
Study Groups	Move-in	Witha	Irawal, cognition	, abuse liability		Move-out
Clonazepam (mg/day)	1.0	2.0	2.0	2.0	2.0	2.0
Placebo (mg/day)	0.0	0.0	0.0	0.0	0.0	0.0

Study Groups	Week 1 Days 6-7 (outpatient)	Weeks 2-7 Days 8-49 (outpatient)	Week 8 Days 50-51 (outpatient taper)	Week 8 Days 52-54 (outpatient taper)	Week 8 Days 55-56 (outpatient taper)	Week 9-12 Days 57-84 (outpatient obervations)
Experimental Group	clonazepam capsules 1 mg twice daily	Clonazeapam capsules 1 mg twice daily	Clonazepam capsules 0.5 mg QAM and 1 mg QHS	Clonazepam capsules 0.5 mg QAM and 0.5 mg QHS	Clonazepam capsules 0.5 mg QHS	No study medication
Placebo Group	Placebo capsules Twice daily	Placebo capsules twice daily	Placebo capsules twice daily	Placebo capsules twice daily	Placebo capsule QHS	No study medication

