Study: # 7343 entitled EFFECT OF CLONAZEPAM ON CANNABIS WITHDRAWAL AND RELAPSE IN TREATMENT-SEEKING PATIENTS: COMBINED INPATIENT/OUTPATIENT STUDY

PI: [name].

NCT# NCT02913924

Statistical Analysis Plan (Grant): 9/19/2013

Amended 4/15/2016 (DSMP)

Grant Submission U54 DA037842: 9/19/2013

3. Data Analysis a. Outcome Measures and Covariates

i. Primary outcome measures: 1) Cannabis use: The time to sustained relapse defined as 5 days of cannabis use over a 7 day period as recorded by the Timeline Followback method and confirmed by creatinine-normalized quantitative urine THC levels, or time to dropout of study, whichever comes first (survival outcome).

ii. Secondary outcome measures: These measures are designed to capture changes in cannabis consumption patterns and other symptoms not measured by the primary outcome measures.

1) Abstinence during the final two weeks (study weeks 11 and 12) of the study (dichotomous)

2) Retention in treatment (survival outcome)

3) Days per week of cannabis use (continuous longitudinal)

4) Cannabis withdrawal: measured by weekly Marijuana Withdrawal Checklist (continuous longitudinal)5) Cannabis craving: measured by weekly Marijuana Craving Questionnaire (continuous longitudinal)

6) Sleep disturbance: measured by the Medical Outcomes Study—Sleep Scale (continuous longitudinal)

iii. Covariates: 1) Demographic characteristics (e.g., gender, age) 2) Baseline severity of cannabis use (measured by the quantity of cannabis per using day at baseline)

iv. Other measures: Adverse effects, as measured by the Systematic Assessment for Treatment and Emergent Events (SAFTEE), will be assessed, including potential effects on compliance and outcome.

b. Sample Size and Randomization: The Research Core will supervise randomization procedures. A total of 72 patients will be recruited over a 2.5-year period and randomized to the double-blind treatment trial, with 36 patients randomized to each of the two treatment groups, nabilone/XR-NTX arm and placebo arm. The randomization sequence will be balanced in blocks of random size (2, 4, 6) to prevent clinicians from guessing what the next patient's treatment might be.

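### SAP Hypothesis 7 names a sleep scale that the protocol does not collect, and the SAP holds two conflicting outcome lists that give sleep and withdrawal different status

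*SAP*

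**What the plan says.** **SAP Section 3.** Item 6 of the secondary list in 3.a.ii reads "6) Sleep disturbance: measured by the Medical Outcomes Study—Sleep Scale (continuous longitudinal"). Hypothesis 7 in 3.e repeats the instrument: the treated group will "experience significantly less sleep disturbance (as measured by the Medical Outcomes Study Sleep scale) compared to subjects in the placebo group". On the model, the SAP says "To test the secondary hypotheses 5, 6, and 7 we will use the same model as in (3"), the mixed model with weekly values for t = 1 to 12. Section 3 is written for nabilone and XR-NTX against placebo, with 72 patients, although the file is headed as the SAP of the clonazepam study.

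**Protocol.** Under Outpatient Study Assessments, the sleep measure is the PSQI, which "will be the primary outcome of sleep quality and length". Table 3 has a row for the "Pittsburgh Sleep Quality Index (PSQI") and no row for any other sleep scale. In the inpatient phase, Study Procedures plans "objective and subjective measures of sleep, and food intake in our Outpatient Marijuana Laboratory". Specific Aims puts sleep inside the first primary outcome: "1) Cannabis withdrawal (mood, sleep quality and duration, food intake"). The secondary outcomes are abuse liability, "Cognitive task performance", and side effects with tolerability.

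**Later parts of the SAP.** A2 gives the same primary and secondary outcomes as the protocol. A4 gives sleep efficiency as an example of a withdrawal symptom that clonazepam should improve. C3 plans repeated measures ANOVA for sleep and names no scale.

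**The concern.** A hypothesis tied to an instrument that nobody administers cannot be tested. Someone must substitute another measure, and unless the substitution is recorded beforehand it may be made with the data in view.

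Sleep is not a side issue in this trial. Disordered sleep is part of the stated rationale for clonazepam, and sleep is a component of the first primary outcome. Yet the SAP treats it as secondary in one place and primary in another, and offers two different analyses. Both 3.d and C3 test at the two-sided 5% level, and no multiplicity adjustment across sleep measures is described. A reader of the final report could not tell which sleep result was the planned one, or what weight it was meant to carry.

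**Working it through.** No figure is stated for Hypothesis 7, so there is nothing to recompute. The check sets the documents side by side.

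**Step 1. Does each Section 3 hypothesis have scheduled data?** All seven name nabilone and XR-NTX. Setting the drug name aside:

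| Hypothesis | Data needed | Protocol source |
|---|---|---|
| 1 relapse, 2 abstinence, 4 days of use | Timeline Followback | Table 3, weekly (urine toxicology also scheduled) |
| 3 retention | Time to dropout | Study records |
| 5 withdrawal | Marijuana Withdrawal Checklist | Table 3, weekly |
| 6 craving | Marijuana Craving Questionnaire | Table 3, weekly |
| 7 sleep | Medical Outcomes Study Sleep Scale | None |

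So 1 of 7 has no data source. Correcting the drug name would repair the other six in this respect but not Hypothesis 7, which needs a correction of its own.

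**Step 2. Count the sleep instruments.**
- Medical Outcomes Study scale: 0 mentions in the protocol and 0 rows in Table 3.
- PSQI: 1 baseline + 12 weekly = 13 scheduled outpatient assessments, and 0 mentions in the SAP.

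**Step 3. Can other sleep data fill the gap?** Model (3) needs a value for each of weeks 1 to 12. The inpatient measures cover days 2 to 5 only, so they cannot supply it. The weekly PSQI can, with no change to the model.

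**Step 4. Compare the outcome lists.**

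| | SAP 3.a.ii | Protocol and SAP A2 |
|---|---|---|
| Secondary outcomes | 6: abstinence in weeks 11–12, retention, days of use, withdrawal, craving, sleep | 3: abuse liability, cognitive performance, side effects and tolerability |
| Withdrawal | Secondary | Primary |
| Sleep | Secondary | Primary, within withdrawal |

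The overlap with the protocol's secondary list is 0 of 6 for 3.a.ii and 3 of 3 for A2. Adverse effects do appear in Section 3, but as another measure (3.a.iv) and as an exploratory analysis (3.e.iii).

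**Step 5. Which analysis applies to sleep?** Section 3 assigns the mixed model and C3 assigns repeated measures ANOVA. C3 also says that primary outcome variables will be examined by mixed models to allow for missing data, which would take in sleep if sleep is primary. No sentence assigns one model to the outpatient data and another to the inpatient data.

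**The case against.** The strongest reply is that the sleep scale is a symptom of something larger: Section 3 was written for another treatment and never adapted, so a wrong instrument in it is unsurprising. The part of the SAP that names clonazepam has its own sleep plan in A4 and C3, and the protocol had already named the PSQI. Much of this stands, and it rules out three stronger readings.

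- A reader might infer that the SAP's secondary outcomes are simply not the trial's. That is true of Section 3 only. A2, in the same file, reproduces the protocol's three. The defect is two lists in conflict.
- A reader might infer that the planned sleep analysis cannot be run. Only Hypothesis 7 lacks data. The C3 ANOVA can be run on the inpatient sleep measures.
- A reader might infer that the choice of sleep measure is wholly open after the data are seen. The protocol names the outpatient measure in advance. What remains open is the PSQI score, the model, and the standing of the inpatient measures.

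The reply does not dispose of the point. The file is headed as this study's SAP. Section 3 is the only part that lists the covariates, describes the randomization blocks and writes out the models, so an analyst has to use it. Replacing the drug name throughout would still leave Hypothesis 7 on an uncollected scale.

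**Conclusion.** Wrong as written, and easily corrected. Leaving aside the drug named in all seven, one of seven Section 3 hypotheses names an instrument with no scheduled data. The six secondary outcomes in 3.a.ii share none with the three in the protocol and A2, and withdrawal and sleep change status between the lists.

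The consequence is ambiguity about which sleep result was planned and how much weight it carries. Sleep data are not lost: the PSQI has 13 scheduled outpatient assessments, and inpatient sleep is measured as well. The root cause is that Section 3 was not adapted to clonazepam.

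The conclusion assumes that Table 3 and the instrument descriptions are the full outpatient schedule. C1 mentions inpatient sleep questionnaires without naming them. Even if one were the Medical Outcomes Study scale, it would not supply weekly values to week 12.

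**What to change.** Amend the SAP before unblinding:

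1. In 3.a.ii item 6 and Hypothesis 7, replace the Medical Outcomes Study scale with the weekly PSQI and pre-specify the score. The documents name no score. The protocol speaks of both quality and length of sleep, so the sponsor should say how each is represented.
2. Keep one outcome list, that of A2 and the protocol. Withdrawal and sleep keep the primary status given in Specific Aims, Outpatient Study Assessments and A2. Label the remaining Section 3 outcomes as additional.
3. Do not relabel the withdrawal checklist or the PSQI as supportive. The protocol designates each as the primary measure of its domain, so that would create a new contradiction.
4. State whether model (3) or the C3 ANOVA governs the outpatient sleep data, and which governs the inpatient sleep data.

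These edits belong with rewriting Section 3 for clonazepam, since changing the scale alone would leave Hypothesis 7 naming the wrong treatment. The cost is SAP wording only: the PSQI is already collected, and no visit, assessment or sample size changes.
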